7.1.2. Planned Primary Efficacy Statistical Analyses

Primary Statistical Analyses
Endpoint

 Time to MACE, defined as the time to first occurrence of CEC-adjudicated MACE (CV death, MI or stroke)
Model Specification

 The primary endpoint will be statistically analyzed using a Cox Proportional Hazards (PH) regression model with treatment group as the only covariate. The SAS PHREG procedure will be used to fit the Cox Proportional Hazards (PH) regression model.
Model Checking & Diagnostics

 Refer to Section 11.12.
Model Results Presentation

 Treatment effect will be estimated via the hazard ratio and associated two-sided 95% Wald confidence interval (CI). The hypothesis of non-inferiority of albiglutide relative to placebo with a margin of 1.3 with respect to cardiovascular risk will be tested at the end of the study when approximately 611 first CEC-adjudicated MACE events have occurred and the projected median duration of subject follow-up is at least 1.5 years. The strength of evidence for non-inferiority will be determined by testing the hypothesis that the observed hazard ratio is significantly different from the null margin of 1.3 (a one-sided $p < 0.025$ for such a test with result in appropriate direction being equivalent to the upper 95% confidence limit for the hazard ratio being less than 1.3) [FDA, 2008]. This test will be based on the Wald statistic. If non-inferiority is established, the hypothesis of superiority of albiglutide relative to placebo will be tested. The product-limit estimates of the probabilities of first MACE over time will be computed and displayed as Kaplan-Meier (KM) curves by treatment group. Cumulative incidence functions will also be computed adjusting for the competing risk of non-CV death [Kalbfleisch, 2002]. A summary of the number and percentage of subjects having first-occurrence MACE will be provided. The number and percentage of the types of events that make up the first occurrence of MACE will also be provided. A summary of all MACE including the number and percentage of subjects and number of events (including first and subsequent MACE) by type of event will be provided. The hazard ratio, two-sided 95% CI, p-value for the statistical non-inferiority test, and p-value for the superiority test will be presented. The number and percentage of subjects with a MACE event and the number censored, the MACE incidence rate per 100 person-years, and the absolute rate difference per 100 person-years and associated 95% CI will be displayed. The hazard ratio, 95% CIs and non-inferiority and superiority p-values will be displayed on a forest plot together with sensitivity analysis results (On-treatment period, On-therapy period, Per-protocol Analysis, Excluding Unknown Cause of Death, Inclusion of Additional Data from Publicly-Available Sources).
Notes:

 The analysis will be based on events positively adjudicated by the CEC and will use the CEC adjudicated event onset dates. First occurrence of adjudicated MACE for a subject is defined as the first adjudicated event, determined by the event date, that is indicated as CV death, MI or stroke. Further details

Primary Statistical Analyses

regarding definitions of events, time to event and time period are provided in Section [11.6.4](#).

- Deaths for which the CEC is unable to establish cause (undetermined cause) will be analyzed as CV deaths except for Analysis Excluding Unknown Cause of Death.
- For subjects who withdraw consent for all follow-up, events occurring up to the date of consent withdrawal will be included in the primary analysis of MACE (i.e. deaths and events collected via publicly available sources subsequent to withdrawal of consent will not be included in the primary analysis but rather in a sensitivity analysis of the primary endpoint).
- Fatal events which are adjudicated to be due to a CV cause, may also have a corresponding CV event adjudicated to determine whether specific endpoint criteria were met (e.g. MI, stroke, heart failure (HF)). Therefore, there may be two adjudication reports for the same fatal CV event. Also, it is possible, for example, that an adjudicated CV death with cause = MI may not meet the adjudication criteria required for MI; and similarly for other fatal events.

Sensitivity and Supportive Statistical Analyses

- As sensitivity analyses, the primary analysis will be repeated based on the On-treatment period (first dose of study treatment to last dose of study treatment) and also based on the On-therapy period (first dose of study treatment to last dose of study treatment + 56 days) using the ITT population, censoring subjects not receiving study treatment at date of randomization.
- A Per-Protocol sensitivity analysis of the primary endpoint will be conducted including all randomized subjects who provide consent and receive at least one dose of study treatment, excluding data after the date of last dose of study treatment + 56 days, and excluding data via censoring for subjects experiencing specified conditions (corresponding definitions are provided in Section [11.1](#)). The Per-Protocol analysis can be viewed as an extension of the On-therapy analysis that in addition accounts for specified conditions.
- Two additional analyses will be conducted in which the primary analysis will be repeated with modifications: one analysis will exclude deaths with unknown cause as events, and the other will include additional data obtained from publicly available sources for subjects who withdrew consent.
- For within-group rates per 100 person-years, the 95% CI will be obtained using an exact Poisson method based on [\[Daly, 1992\]](#) following [\[Fleiss, 2003\]](#). For the difference in rates between treatments, the 95% CI will be constructed with a Normal approximation using Wald's method [\[Liu, 2006\]](#).
- A tipping point analysis of the primary endpoint will be conducted to explore the sensitivity of the primary analysis results to potentially different event hazard rates in study non-completers as compared to completers. Assuming a proportional hazards relationship for MACE hazard rates in non-completers vs. completers, the hazard ratio between albiglutide and placebo arms can be expressed as a function of several parameters: probability of non-completion, treatment hazard ratio among completers, survival functions in completers (all estimated from the data), and hazard ratios for completers vs non-completers in each arm (c_0 in the placebo arm and c_1 in the albiglutide arm, both of which are varied across a range of values). Non-inferiority would not be met for values c_0 and of c_1 such that the upper limit of the 95% Wald confidence interval for hazard ratio exceeds 1.3. The results of this analysis will be displayed graphically as a grid of points corresponding to different combinations (c_0, c_1), where plotting symbols are used to indicate whether or not non-inferiority was met at each combination.
- Recurrent event analyses of MACE, MI and Stroke will be conducted using the negative binomial regression model which is an extension of Poisson regression [\[Agresti, 2002\]](#). In

Sensitivity and Supportive Statistical Analyses

particular, each subject is assumed to have events generated by a Poisson process with subject-specific rates which are distributed according to a gamma distribution. The negative binomial regression model is an event count based model that does not assume an equal mean and variance across subjects and allows for overdispersion in the data, which occurs when the variance is greater than the conditional mean. The MACE event rates will be analysed using a negative binomial generalized linear model with a log link function using SAS PROC GENMOD. The model will include a term for treatment group. The log of follow-up time will be used as an offset. The estimated mean rates will be presented by treatment group along with treatment ratios of albiglutide vs. placebo and associated p-values and 95% confidence limits. If difficulties are encountered in fitting the negative binomial model (e.g. lack of convergence), then use of alternative approaches such as Poisson regression will be considered.

- For MACE, subgroup analyses will be performed for the subgroups of interest identified in Section 11.10 using a Cox PH model including treatment group, the subgroup of interest and the subgroup by treatment interaction. The hazard ratio and associated 95% confidence interval for the treatment effect for MACE will be provided for each subgroup level for which analysis is performed as well as p-value for subgroup by treatment interaction. The interaction will be assessed using a nominal alpha level of 0.10. A forest plot will graphically display the results of these analyses for the subgroup levels of interest. As the number of subgroup variables may be large, the probability of observing at least one nominally statistically significant result may be high; no formal conclusions will be drawn based on the results of these analyses.
- In the event an investigator and/or any member of their staff is documented to have improper or poor study conduct (such as audit findings indicative of data irregularities), analyses may be performed as described next. All data will be included in the primary analyses. Separate summaries and analyses will be performed with the exclusion of all subjects at the noted site(s). At a minimum, the summaries and analyses excluding the noted site(s) will include the primary analysis of the primary endpoint.

8. SECONDARY STATISTICAL ANALYSES

8.1. Secondary Efficacy Analyses

8.1.1. Overview of Planned Secondary Efficacy Analyses

The secondary efficacy analyses will be based on the ITT population, unless otherwise specified.

[Table 6](#) provides an overview of the planned secondary efficacy analyses, with further details of data displays being presented in Section [11.15](#).

Table 6 Overview of Planned Secondary Efficacy Analyses

Endpoints	Absolute						Change from Baseline							
	Stats Analysis			Summary		Individual		Stats Analysis			Summary		Individual	
	T	F	L	T	F	F	L	T	F	L	T	F	F	L
CV Endpoints														
Secondary efficacy CV endpoints				Y (x2) [1]										
Time to MACE or Revascularization [2], Time to CV Death, Time to MI, Time to Stroke, Time to CV Death or HF hospitalization [3]	Y (x5)	Y (x7)	Y (x5)											
Supplemental Time to MI , Supplemental Time to Stroke	Y (x2)													
Percutaneous Intervention, Coronary Artery Bypass Graft, Catheterization				Y (x4) [4]										
Details for Adjudicated Events				Y (x3) [5]										
Events That Do Not Meet CV Endpoint or TIA Definition				Y (x2)										
Metabolic Endpoints														
Time to Insulin [6], Time to Prandial Insulin [7]	Y (x2)	Y (x2)	Y (x2)											
Proportion of subjects achieving composite metabolic endpoint [8]	Y		Y											
Proportion of subjects	Y													

Endpoints	Absolute								Change from Baseline						
	Stats Analysis			Summary		Individual			Stats Analysis			Summary		Individual	
	T	F	L	T	F	F	L	T	F	L	T	F	F	L	
achieving composite metabolic endpoint [8] – On-treatment period															
Time to Microvascular event [9]	Y	Y	Y	Y (x2) [10]											
HbA1c – OC [11,12]				Y (x2) [13]	Y						Y		Y		
HbA1c ≤ 7.0 %, Central Lab only				Y											
HbA1c – OC [11,12] – 8 monthly assessments only								Y (x2) [13]			Y (x2) [14]				
HbA1c – OC [11,12] – On-treatment period – 8 monthly assessments only								Y (x2) [13]			Y				
HbA1c – OC [11] – 8 monthly assessments only, Central lab only								Y (x2) [13]							
Body weight – OC [11]				Y	Y						Y		Y		
Body weight - OC [11] - 8 monthly assessments only								Y			Y (x2) [14]				
Body weight – OC [11] – On-treatment period 8 monthly assessments only								Y			Y				

NOTES :

- T = Table, F = Figure, L = Listing, Y = Yes display generated.
- Stats Analysis = Represents TFL related to any formal statistical analyses (i.e. modelling) conducted.
- Summary = Represents TFL related to any summaries (i.e. descriptive statistics) of the observed raw data.
- Individual = Represents FL related to any displays of individual subject observed raw data.

[1] Incidence of all in one summary, incidence of first occurrence of composite endpoints in one summary.

[2] Time to first occurrence of adjudicated MACE or urgent revascularization for unstable angina.

[3] Time to adjudicated CV death or hospitalization due to heart failure.

[4] Incidence of all in one summary, and also separate summary of details for each intervention.

[5] Death, MI, stroke.

[6] Time to initiation of insulin of more than 3 months duration for those subjects not treated with insulin at study start (NIN population).

[7] Time to initiation of prandial insulin of more than 3 months duration in those subjects on basal insulin at study start (BIN population).

[8] Proportion of subjects achieving glycaemic control (HbA1c ≤ 7.0% at final assessment) with no severe hypoglycaemic incidents and weight gain <5% of body weight.

[9] Time to first occurrence of a clinically important microvascular event (see Section 11.6.4).

- [10] Incidence of all in one summary, incidence of first occurrence in one summary.
- [11] OC = Observed Case (see [Appendix 7](#)).
- [12] Including baseline local and Central lab data and post-baseline scheduled visit Central lab data.
- [13] HbA1c to be summarized for units=% and also units=mmol/mol.
- [14] Plots of raw means vs time and also adjusted means vs time.

8.1.2. Planned Secondary Efficacy Statistical Analyses

Statistical Analyses
Endpoints

 • Time to MACE or Revascularization = Time to first occurrence of adjudicated MACE or urgent revascularization for unstable angina (UA) • Time to CV Death = Time to adjudicated CV Death • Time to MI = Time to first occurrence of adjudicated MI • Time to Stroke = Time to first occurrence of adjudicated Stroke • Time to CV Death or HF Hospitalization = Time to first occurrence of adjudicated CV Death or HF Hospitalization • Time to Insulin = Time to initiation of insulin of more than 3 months duration (NI population) • Time to Prandial Insulin = Time to initiation of prandial insulin of more than 3 months duration (BI population) • Proportion of subjects achieving composite metabolic endpoint (glycaemic control (HbA1c≤ 7.0% at final assessment) with no severe hypoglycaemic incidents and weight gain <5% from baseline) • Time to Microvascular Event = Time to first occurrence of a clinically important Microvascular Event (see Section 11.6.4) • Change from baseline in HbA1c • Change from baseline in body weight
Model Specification

 • Analyses of time to event endpoints will be done in a similar manner as the primary endpoint: treatment group comparisons will be done using a Cox Proportional Hazards regression model. The analysis will compare time to event using a Wald test evaluated at the two-sided 5% significance level. The p-value, estimated hazard ratio and associated 95% Wald confidence interval will be obtained using a Cox PH model with treatment group as the only covariate. The SAS PHREG procedure will be used to fit the Cox PH regression model. • For time to first occurrence of adjudicated MI, events will include adjudicated MI or death with adjudicated cause = MI. In a similar manner, for time to first occurrence of adjudicated stroke, events will include adjudicated stroke or death with adjudicated cause = stroke. • Supplemental analysis of time to MI will be done including adjudicated MI events but excluding events which do not meet the adjudication criteria for MI but are classified by the CEC as deaths due to MI. This analysis will be done in a similar manner as the primary endpoint. Similarly, a supplemental analysis of time to stroke will be done including adjudicated stroke events but excluding events which do not meet the adjudication criteria for stroke but are classified by the CEC as deaths due to stroke. • For the composite metabolic endpoint, treatment group comparisons will be done with the nonparametric, covariance-adjusted, extended Mantel-Haenszel test using the SAS FREQ procedure. Covariates will include baseline HbA1c (<8.0% versus ≥ 8.0%) and prior diabetes

Statistical Analyses

therapy (diet and exercise alone versus all other therapies). As a sensitivity analysis, this will also be done for the On-treatment period excluding subjects who did not receive at least one dose of study treatment.

- Summaries of HbA1c by visit will be provided by the following categories: $\leq 6.5\%$, $> 6.5 - 7.0\%$, $> 7.0 - 8.0\%$, $> 8.0 - 9.0\%$, $> 9.0\%$.
- For change from baseline HbA1c and change from baseline body weight, treatment group comparisons will be done using a mixed model repeated measures (MMRM) analysis including Observed Case data from the Month 8 and Month 16 scheduled post-baseline assessments [Mallinckrodt, 2008]. PROC MIXED in SAS [Littell, 1996] will be used to fit the model, using the restricted maximum likelihood estimation method and the Kenward-Roger option to estimate denominator degrees of freedom and standard errors. An unstructured covariance structure will be used to model the within-subject errors, shared across treatments. If the analysis using an unstructured covariance structure does not converge, analyses using AR(1) or other covariance structures will be considered. Missing data will be assumed to be missing at random. Analyses will include the fixed, categorical effects of treatment, visit, and treatment-by-visit interaction, as well as the continuous, fixed covariates of baseline and baseline-by-visit interaction. Due to the event-driven nature of the study, beyond Month 16 only summary statistics will be provided. For these two endpoints the primary treatment comparison will be the contrast between treatments (Albiglutide - Placebo) at the Month 16 visit using the two-sided p-value from the corresponding t-test at $\alpha=0.05$. As sensitivity analyses, these will also be done for the On-treatment period excluding subjects who did not receive at least one dose of study treatment.

Model Checking & Diagnostics

- Refer to Section 11.12.

Model Results Presentation

- For time to event endpoints, p-values and estimates of hazard ratios and 95% confidence intervals (CIs) will be presented, along with Kaplan-Meier (KM) curves by treatment group. For time to MI and time to stroke, cumulative incidence functions will also be computed adjusting for the competing risk of death.
- For change from baseline endpoints, least square means, 95% CIs and nominal p-values will be presented, along with plots of least square means vs time by treatment group.

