Time to Event endpoints
Metabolic Management Events

 Time to insulin and time to prandial insulin are defined as follows: For subjects with an event, time to event is the initiation date – treatment start date + 1. For subjects with no event, time to event (censored) is the censor date – treatment start date +1. 
For subjects not receiving any study treatment, who therefore have no treatment start date, time to event will be determined based on date of randomization.
 
The censor date is the latest of clinic visits and phone calls.
 
The definitions of these events are provided in Section 2 of the protocol. Following are more detailed descriptions of event determination:
 
 An insulin event will require more than 3 months use of insulin for subjects in the NI population and will be determined based on data recorded in the Concomitant Medications eCRF form. Specifically this will require use of any type of insulin for a continuous duration of > 3 months (ie > 3*30.4375 days); this could involve multiple medication entries in the eCRF. In the determination of continuous duration of > 3 months, gaps in useage < 7 days will not be considered a break, but gaps in useage \geq 7 days will be considered a break. A prandial insulin event will require more than 3 months use of prandial insulin (i.e., either a prandial-only insulin or a mixed insulin) for subjects in the BI population and will be determined based on data recorded in the Concomitant Medications eCRF form. Specifically this will require use of prandial or mixed insulin for a continuous duration of > 3 months (ie > 3*30.4375 days); this could involve multiple medication entries in the eCRF. In the determination of continuous duration of > 3 months, gaps in useage < 7 days will not be considered a break, but gaps in useage \geq 7 days will be considered a break. Insulin categories are shown in Section 11.13. Initiation date is the date of the earliest medication use after treatment start date. Duration of use = latest stop date of medication – initiation date +1. If a medication stop date is missing, then the date of study completion will be used. 
 Time to first occurrence of a clinically important microvascular event is defined as follows: For subjects with an event, time to event is the first event date – date of randomization +1. For subjects with no event, time to event (censored) is the censor date – date of randomization +1. 
The censor date is the latest of clinic visits and phone calls.
 
The first event date is the date of first occurrence of a clinically important microvascular event. The definition of clinically important microvascular events is provided in Section 6.2.4 of the protocol. Based on this definition, such an event will be determined by one or more of the following items being recorded in the eCRF with a date on or after date of randomization:
 
 Need for renal transplant or dialysis (Renal Impairment eCRF form, Event Treatment/Management: “Treatment required for the renal impairment” = “Renal transplantation”, “Haemodialysis”, or “Peritoneal dialysis”); event date is the corresponding treatment start date. Temporary renal replacement therapy will not

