2.37	Summary of All Adjudicated Stroke Event Details (CV Follow-up Time Period)	ITT	
2.38	Summary of All Adjudicated Stroke or TIA Events (CV Follow-up Time Period)	ITT	
2.39	Summary of All Adjudicated TIA Events (CV Follow-up Time Period)	ITT	
2.40	Summary of Time to First Occurrence of Adjudicated Stroke or TIA (CV Follow-up Time Period)	ITT	No p-values

Table No.	Title	Population	Programming note
2.41	Summary of Time to First Occurrence of Adjudicated TIA (CV Follow-up Time Period)	ITT	No p-values
2.42	Summary of Concordance Between Investigator Reported and Adjudicated Efficacy Endpoints (CV Follow-up Time Period)	ITT	<by variable> = Total, Albi and Placebo
2.43	Summary of Concordance Between Investigator Reported and Adjudicated MACE (CV Follow-up Time Period)	ITT	
2.44	Summary of Concordance Between Investigator Reported and Adjudicated Death Events (Vital Status Follow-up Time Period)	ITT	
2.45	Summary of Concordance Between Investigator Reported and Adjudicated Myocardial Infarction and Unstable Angina Requiring Urgent Revascularization Events (CV Follow-up Time Period)	ITT	
2.46	Summary of Concordance Between Investigator Reported and Adjudicated Stroke and TIA (CV Follow-up Time Period)	ITT	
2.47	Summary of Concordance Between Investigator Reported and Adjudicated Individual Endpoint Events (CV Follow-up Time Period)	ITT	
2.48	Summary of Events Other than Deaths That Do Not Meet CV Endpoint or TIA Definition (CV Follow-up Time Period)	ITT	
2.49	Summary of Events That Do Not Meet CV Endpoint or TIA Definition by Investigator-reported Event Type (CV Follow-up Time Period)	ITT	
2.50	Summary of Analysis of Time to Initiation of Insulin of More Than 3 Months Duration For Subjects Not Treated With Insulin At Study Start	NI	Include HR, 95% CI, superiority p-value.
2.51	Summary of Analysis of Time to Initiation of Prandial Insulin of More Than 3 Months Duration For Subjects on Basal Insulin at Study Start	BI	Include HR, 95% CI, superiority p-value.
2.52	Summary of Mantel-Haenszel Analysis of Composite Metabolic	ITT	p-value only at 8 monthly visits

Table No.	Title	Population	Programming note
	Endpoint Stratified by Baseline HbA1c and Prior Diabetes Therapy		(i.e. Month 8, 16, 24 ..) and Final Assessment

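### Adding baseline HbA1c to the Cox models for time to insulin and time to prandial insulin would gain a little power at no cost in type I error; the planned treatment-only test is valid.

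*SAP*

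**What the plan says.** Section 8.1.2 lists time to insulin and time to prandial insulin with the secondary cardiovascular time-to-event endpoints and handles all of them like the primary endpoint. The comparison is a "Wald test evaluated at the two-sided 5% significance level", and the p-value, hazard ratio and interval are "obtained using a Cox PH model with treatment group as the only covariate".

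Section 11.6.4 defines the events by duration of use (for example, "An insulin event will require more than 3 months use of insulin for subjects in the NI population") and adds nothing about the model. The programming note for Tables 2.50 and 2.51 in section 11.15.4 reads "Include HR, 95% CI, superiority p-value", and no adjusted version is listed. The stratified Cox model in section 11.12.1 is named only for first MACE, and only as an option if hazards look non-proportional. The section 11.10.1 subgroup analyses concern the primary endpoint.

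In the same section 8.1.2, the test of the composite metabolic endpoint does use baseline glycaemia: "Covariates will include baseline HbA1c (<8.0% versus ≥ 8.0%) and prior diabetes" therapy. The repeated-measures model for change in HbA1c has the "continuous, fixed covariates of baseline and baseline-by-visit interaction".

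**The concern.** Starting insulin for more than three months is a decision about glycaemic treatment, so the HbA1c at which a subject enters the trial can be expected to predict it. The SAP applies the cardiovascular model to this endpoint without comment. Elsewhere it does adjust secondary analyses for expected predictors: section 8.2.2 adds an analysis of severe hypoglycaemia stratified by baseline sulfonylurea/insulin use, and tests malignant neoplasms adjusting for baseline insulin use and for history of malignancy.

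Leaving a prognostic covariate out of a Cox model costs power. The two insulin endpoints are also analysed in subsets of the trial, where there is less power to spare. At stake is the precision of the evidence on whether albiglutide delays insulin. The covariate needs no new data: HbA1c is scheduled at screening (11.2.1), has a baseline definition (11.5.2.1) and is already categorised (11.10.1).

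**Working it through.** **1. The plan's own figure.** The SAP's only power statement is for MACE: 611 events, 90% power, margin 1.3, true hazard ratio 1.0, two-sided alpha 0.05, 1:1 allocation. Schoenfeld's formula gives 4 × (1.960 + 1.282)² / (ln 1.3)² = 610.6, rounded up to 611. It reproduces. There is no corresponding figure for the insulin endpoints.

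**2. Inputs that must be assumed.** The SAP gives no size for either subset, no insulin event rate, no target hazard ratio and no strength of HbA1c as a predictor. The main setting assumes:
- 800 subjects per arm and a hazard ratio conditional on HbA1c of 0.60;
- follow-up uniform on 1.0 to 2.2 years (mean 1.6, in line with the planned median of at least 1.5);
- exponential event times with a mean placebo hazard of 8 or 15 per 100 person-years;
- standardised HbA1c acting linearly on the log hazard with SD 0.3 (weak), 0.6 (moderate) or 0.9 (strong). As hazard ratios per SD of HbA1c these are exp(0.3) = 1.35, exp(0.6) = 1.82 and exp(0.9) = 2.46.

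As a rough check on event fractions at mean follow-up: 1 − exp(−0.08 × 1.6) = 12% on placebo and 1 − exp(−0.08 × 0.60 × 1.6) = 7% on albiglutide, about 10% overall. At hazard 15 the figures are 21% and 13%, about 17% overall. Variation in HbA1c lowers these slightly, which gives the range 9-17%.

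**3. Gain in effective sample size.** This is (mean adjusted Z / mean unadjusted Z)², with 600 simulated trials per setting.

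| HbA1c effect | Gain |
|---|---|
| weak | about 1-2% |
| moderate | about 4-8% |
| strong | about 12-18% |

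The power gain is 0 to about 5 points. With the strong effect and 16% of subjects with events, the treatment-only model gives 0.622 against the conditional 0.60, a gap of 0.02.

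**4. Second set of assumptions**, with 2,500 trials per row, the same follow-up and 20% placebo incidence. Each cell gives treatment-only → adjusted.

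| Total N, conditional HR | HR per SD of HbA1c | Estimated HR | Power |
|---|---|---|---|
| 3000, 0.75 | 1.3 | 0.752 → 0.750 | 89.9% → 90.3% |
| 3000, 0.75 | 1.6 | 0.753 → 0.749 | 89.4% → 90.7% |
| 3000, 0.75 | 2.0 | 0.761 → 0.750 | 87.9% → 91.2% |
| 3000, 0.75 | 2.5 | 0.772 → 0.751 | 85.0% → 91.6% |
| 1500, 0.70 | 1.3 | 0.704 → 0.703 | 79.5% → 79.8% |
| 1500, 0.70 | 2.0 | 0.712 → 0.699 | 77.6% → 81.4% |
| 1500, 0.70 | 2.5 | 0.722 → 0.700 | 73.6% → 81.3% |

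The gain runs from 0.3 to 7.7 points. With 10% placebo incidence and N = 3000 it is 0.4 to 4.2 points. A two-category HbA1c (assumed cut at −0.4 SD) recovers only part: at N = 1500 and 2.5 per SD, power is 75.6%, between 73.6% and 81.3%.

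**5. Type I error.** With a true hazard ratio of 1.0, rejection rates were about 4-6% both with and without the covariate.

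**The case against.** The strongest reply is that nothing here is wrong. The SAP states one explicit rule for all its Cox models, the rule is valid, and section 11.11.1 treats these endpoints as supportive, with nominal p-values. All of that stands, and it limits the point to an optional improvement.

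Three stronger readings are tempting, and the SAP does not support them.

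- *That the planned hazard ratio is biased towards 1.* In a randomised comparison the treatment-only model estimates a marginal hazard ratio. The conditional ratio is a different quantity, and the gap between them is non-collapsibility. Neither is the single correct value.
- *That the plan contradicts itself by adjusting its other glycaemic endpoints.* The plan is consistent by endpoint type: MACE, the secondary cardiovascular endpoints, microvascular events, death and stroke/TIA all get treatment-only Cox models. The baseline term in the HbA1c repeated-measures model is that endpoint's own baseline, and body weight uses baseline weight. The composite metabolic endpoint is the only direct precedent, and a limited one, because HbA1c of 7.0% or less is part of its response definition.
- *That chance imbalance invalidates the subset comparisons.* Ordinary standard errors already allow for it. With 800 per arm the standard error of the mean difference is √(2/800) = 0.05 SD. A two-standard-error imbalance of 0.1 SD would move the hazard ratio by a factor of about 1.3^0.1 = 1.03 to 2.0^0.1 = 1.07. Adjustment would remove most of that variation, which is a gain in precision and not a repair of validity.

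The size also depends wholly on assumed inputs, and with a weakly prognostic HbA1c it is negligible.

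**Conclusion.** The point holds as an efficiency improvement of low severity. The two insulin analyses leave out a baseline measurement that the trial already has and that plausibly predicts the event. Including it can be expected to raise power without affecting type I error. Under the main assumptions, the benefit is equivalent to about 1-2% more subjects at the weak end and 12-18% more at the strong end. The strength of HbA1c as a predictor matters most to this range, and the SAP does not give it. The shift of up to about 0.02 in the hazard ratio applies to event fractions of roughly 9-17% and would be larger if insulin starts were much more common. The direction of the gain depends only on HbA1c being prognostic. No confirmatory claim rests on these endpoints, and the MACE non-inferiority and superiority tests are untouched.

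**What to change.** Before unblinding, amend section 8.1.2 for these two endpoints only:

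- Fit the Cox model with treatment and continuous baseline HbA1c (as defined in section 11.5.2.1), and report it as the main result in Tables 2.50 and 2.51.
- State that the hazard ratio is then conditional on baseline HbA1c.
- State how missing baseline values are handled. Otherwise those subjects drop out of the fit. Imputing the subset mean pooled over arms is one simple option; a missing category would serve if HbA1c were entered in categories.
- Keep the treatment-only hazard ratio, interval and p-value as a supportive row in each table, so that the marginal estimate remains available.

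Stratifying by the three HbA1c categories of section 11.10.1 is an acceptable alternative, although categorising gives up some of the gain.

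The cost is a few sentences of SAP text and one extra row in each of two tables. No data collection changes. The price is a change of main estimand for these endpoints, which is why the choice should be fixed in advance: adding the covariate after unblinding would look data-driven.
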